various health insurance plans. The cost for individuals who do not qualify for health insurance coverage will come from the study budget. Participants will be instructed to export from the app a weekly data use report to the research physician's Montefiore email. The research physician will be linked to participant usage and progress through the app. There is an emergency resources section within the app that includes information on crisis help-lines and other resources for users in emergency situations. The app is available for use in iOS and Android systems as well as online through any web browser. App content is available in English with text translations in Spanish.

All participants will receive a unique link to complete a follow-up questionnaire at 48 weeks post intervention (Table 1). Non-responders will receive a reminder phone call twice weekly for 2 weeks and thereafter be considered lost to follow-up.

Table 1. Timeline and Sources of Data		
Baseline - REDCap Questionnaire (completed by patient at office visit or remotely)		
Socio-demographics	Assessment Tools	Clinical features

 ▪ Age ▪ Race/ethnicity ▪ Sex ▪ Birthplace ▪ Primary language ▪ Educational attainment ▪ Employment status ▪ Health insurance ▪ Marital status 	
 ▪ IBD disease activity index: Short Crohn's Disease Activity Index for Crohn's disease or Simple Clinical Colitis Activity Index for ulcerative colitis ▪ PROMIS-29 ▪ Perceived Stress Scale ▪ PROMIS Self-efficacy Managing Emotions ▪ PhenX Toolkit – Spirituality ▪ Brief Resilient Coping Scale 	
 ▪ IBD phenotype ▪ Disease duration ▪ IBD medications ▪ Previous/current psychiatric diagnosis, suicidal ideation or hospitalization
Follow-up at 84 weeks REDCap Questionnaire (completed by patient remotely)		
	Assessment Tools	
	
 ▪ IBD disease activity index: Short Crohn's Disease Activity Index for Crohn's disease or Simple Clinical Colitis Activity Index for ulcerative colitis ▪ PROMIS-29 ▪ Perceived Stress Scale ▪ PROMIS Self-efficacy Managing Emotions 	

3) Study Population

We aim to recruit 25 patients in each study arm for a total of 50 participants. Eligibility will be restricted to:

- age \geq 18 years
- race/ethnicity self-identified as Black/African American or Hispanic/Latinx
- established diagnosis of Crohn's disease or ulcerative colitis

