Primary analysis will be by intention-to-treat with participants analyzed in the group to which they were randomized. We will use descriptive statistics to summarize socio-demographic and disease characteristics of both study groups and of app usage in the iCBT group: number of modules completed; weekly time spent on app; participation in community support groups. Our primary hypothesis is that participants in the iCBT group will have lower psychological distress scores compared to those in the digital mood tracking group post-intervention. To test the association between psychological distress (T-score for anxiety, depression) and study group, we will use Student's t-test if the normality assumption is met, or the Mann-Whitney U test if normality is appreciably violated. Assuming a minimum clinically significant change of a 5.5 points difference in T-scores between study groups with a standard deviation of \pm 6 points, a sample size of 40 participants (20 in each arm) will be needed to have 80% power at an alpha of 0.05. Targeting a recruitment sample size of 50 participants (25 in each arm) would allow for roughly 20% drop-out rate.

Our secondary hypotheses are that participants in the iCBT group will have lower perceived stress scores and higher HRQoL. To test these hypotheses, we will again use Student's t-test if the normality assumption is met or the Mann-Whitney U test if normality is appreciably violated. Finally, we hypothesize that elevated disease activity at baseline (Short Crohn's Disease Activity Index \geq 150 or Mayo sub-scores \geq 2) will be associated with achieving a minimum clinically significant change in T-score. To test the association between high baseline disease activity and minimum clinically significant change (as a dichotomous outcome), we will perform Chi-squared or Fisher's exact test.

Aim 2: Evaluate implementation of iCBT among Black and Latinx IBD patients

Participants randomized to iCBT will complete a survey as part of their follow-up assessment at 84 weeks to evaluate their acceptance of and satisfaction with iCBT.

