Participants will have the option to complete the post-intervention survey at the study site or off-site on their own personal device. Survey responses will be recorded and stored in REDCap. Participants will be asked a series of questions aimed at evaluating attitudes about receiving psychotherapy via a mobile application and how useful they found iCBT. Likert scale from strongly agree to strongly disagree will be used. At the end of the survey, participants will be invited to participate in semi-structured interviews. The interviews will be conducted by the research physician to elicit personal and logistical factors that may have influenced participant iCBT use.

Post-intervention surveys will be categorized with respect to level of participant acceptance of iCBT, while app usage will be analyzed as continuous (e.g. time spent on

app) and categorical (e.g. used during all 48 weeks). We hypothesize that participants more likely to accept iCBT will be those with: high self-efficacy (T-score above the mean of 50) compared to low self-efficacy (T-score at or below the mean of 50); high coping (Brief Resilient Coping Scale score ≥ 17) compared to low coping (score < 17); high spirituality (score ≥ 16) compared to low spirituality (score < 16); younger age (less than 40 years) compared to older age (at or over 40 years); higher educational attainment (high school graduate) compared to lower educational attainment (less than high school); recently diagnosed (within 2 years) compared to longstanding disease (over 2 years); and high disease activity (Short Crohn's Disease Activity Index ≥ 150 or Mayo sub-scores ≥ 2) compared to low disease activity (Short Crohn's Disease Activity Index < 150 or Mayo sub-scores < 2). We will use descriptive statistics to summarize behavioral, socio-demographic and clinical factors associated with iCBT acceptance and greater app usage, and we will perform Chi-squared or Fischer's exact tests to examine the associations. Interview responses will be examined for themes, and individual and process level barriers and facilitators to iCBT use will be summarized with respect to potentially modifiable features.

8) Data quality control and database management.

All study questionnaire responses will be entered and stored on REDCap, which will be password protected and accessed only by the research study team. Deidentified data from REDCap will be exported and analyzed on statistical software (e.g. Stata).

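### Aim 2 tests six numeric predictors only as two groups, with chi-squared or Fisher's exact tests in about 20–25 iCBT participants, and names no test for continuous app usage

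*Combined protocol and SAP*

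**What the plan says.** Section 7 (Data Analysis), Aim 2, lists seven factors expected to go with acceptance of iCBT, each as a two-group contrast. Six are measured on a numeric or ordered scale: self-efficacy T-score (cut at 50), Brief Resilient Coping Scale (17), spirituality score (16), age ("younger age (less than 40 years) compared to older age (at or over 40 years"), time since diagnosis (2 years) and disease activity (150 on the Crohn's index, or 2 on Mayo sub-scores). The seventh, education, is categorical to begin with.

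There are two outcomes. Survey answers on a Likert scale are to be sorted into levels of acceptance; the number of levels and the boundaries are not given. For use of the app, the plan says "app usage will be analyzed as continuous (e.g. time spent on", and the sentence goes on, across a page break, to say that usage will be categorical as well, with use in all 48 weeks as the example.

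The methods named are descriptive statistics plus chi-squared or Fisher's "exact tests to examine the associations". The t-test and the Mann–Whitney test are named only under Aim 1.

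The analysis set is one arm: "Participants randomized to iCBT will complete a survey as part of their follow-up assessment at 84 weeks". Section 3 gives its size: "We aim to recruit 25 patients in each study arm for a total of 50 participants". No power or sample size is stated for Aim 2.

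**The concern.** Two things are at issue.

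The first can be seen on the page. Usage is declared a continuous variable, but neither named test can relate a predictor to a continuous outcome. The plan therefore states an analysis without a method for it, and the method would be chosen after the data are seen.

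The second is loss of information. A 40-year-old and a 75-year-old count as the same, and a 39-year-old and a 40-year-old as different. In a large study this costs some precision. With 20–25 people it can decide whether a real association is detected. Aim 2 is one of the trial's two aims, and Section 2 predicts which factors will relate most strongly to acceptance. Separate p-values from 2x2 tables do not rank strength; correlations with confidence intervals put the numeric predictors on a common scale.

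**Working it through.** **Size of the analysis set.** The plan's only sample-size figure is for Aim 1, and it reproduces. Inputs from Section 7, Aim 1: "Assuming a minimum clinically significant change of a 5.5 points difference in T-scores between study groups" with SD 6, 80% power and alpha 0.05 (taken as two-sided, since the plan does not say).

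- Normal approximation: n per arm = 2 × (1.960 + 0.842)² × 6² / 5.5² = 18.7, so 19.
- t-based solution: 19.7, so 20 per arm, with power 0.806 at 20. This matches the plan's 40.
- Drop-out: 40 / (1 − 0.20) = 50, as stated ("Targeting a recruitment sample size of 50 participants (25 in each arm) would allow for roughly 20% drop-out rate").
- Aim 2 uses the iCBT arm only: 25 at most, and 25 × 0.8 = 20 after drop-out.

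**Which test would apply.** The plan gives no rule for choosing between the two tests. With 20 people split 10/10 on both variables, each expected cell count is 10 × 10 / 20 = 5. If 20% are in the high-predictor group and half accept, the smallest is 4 × 10 / 20 = 2. Fisher's test is thus a realistic choice for many of these tables, but not for certain all of them, so both tests are shown.

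**Power.** The documents give no correlation, no share above each cut and no acceptance rate. Assumed: predictor and outcome jointly normal, correlation r of 0.5 or 0.6, cuts at the population median, two-sided alpha 0.05, one predictor at a time. The first three power columns come from 4,000 simulated trials per setting (standard error at most √(0.25/4000) = 0.008). The chi-squared column, without continuity correction, comes from a separate run of 10,000.

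| n | r | Spearman, both numeric | Mann–Whitney, outcome yes/no | Fisher, both cut | Chi-squared, both cut |
|---|---|---|---|---|---|
| 20 | 0.5 | 0.576 | 0.393 | 0.190 | 0.315 |
| 25 | 0.5 | 0.672 | 0.493 | 0.341 | 0.391 |
| 20 | 0.6 | 0.762 | 0.558 | 0.306 | 0.441 |
| 25 | 0.6 | 0.867 | 0.686 | 0.494 | 0.547 |

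Relative loss = 1 − (power after cutting / power before). Rows are in the same order as above.

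| Comparison | n=20, r=0.5 | n=25, r=0.5 | n=20, r=0.6 | n=25, r=0.6 |
|---|---|---|---|---|
| Both cut, Fisher against Spearman | 67% | 49% | 60% | 43% |
| Both cut, chi-squared against Spearman | 45% | 42% | 42% | 37% |
| Predictor cut only, Fisher against Mann–Whitney | 52% | 31% | 45% | 28% |
| Predictor cut only, chi-squared against Mann–Whitney | 20% | 21% | 21% | 20% |

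For example, 1 − 0.190/0.576 = 67%. Repeat runs move these by a few points. At r = 0.5, one gave Spearman 57% and chi-squared 30% at n = 20 (loss 1 − 30/57 = 47%), and 68% and 37% at n = 25 (46%). Another gave Mann–Whitney 0.488 and chi-squared 0.380 at n = 25 (loss 22%). Hence the ranges 37–47% and 20–22% for chi-squared.

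**Unequal groups.** The plan's cuts are fixed values, so the groups need not be equal. At r = 0.5 with 20% in the high-predictor group, Fisher's power is 0.108 (n = 20) and 0.172 (n = 25), against 0.196 and 0.344 with equal groups in the same run. Chi-squared falls too, from 0.315 to 0.211 and from 0.391 to 0.269.

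**The case against.** Several points on the other side are sound.

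- A reader might infer that the plan wastes most of its power. The documents do not support that as a general statement. The loss depends on correlations and split shares that they do not give, and on which test is used. With median cuts it exceeds half under Fisher at n = 20 when both variables are cut. It is below half under chi-squared throughout, and in most settings when only the predictor is cut. The second comparison is the fair one for acceptance, because the plan already intends to categorise it.
- A reader might infer that usage can only be analysed by cutting it. The plan itself provides for categorical usage alongside continuous usage, and descriptive statistics can summarise time on the app. The gap is narrower: no test is named for the continuous form.
- A reader might infer that finding no predictor at all is the likely result. Single-predictor power does not show that. If three roughly independent predictors each had r = 0.5, Fisher's test would find at least one with probability 1 − (1 − 0.190)³ = 47% at n = 20 and 1 − (1 − 0.341)³ = 71% at n = 25.
- Aim 2 also rests on descriptive summaries and interviews, which these tests do not affect. The plan claims no power for it, and sample size remains the main limit: Spearman reaches only 58–67% at r = 0.5.
- Two-group results are easy to read, and a Likert total presumes that the items form one scale, which the plan does not establish.

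All of this limits the claim about size. It does not supply the missing test, and it gives no reason to discard numeric information that will already have been collected.

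**Conclusion.** The point holds. Six numeric predictors are tested only as two groups, with tests for contingency tables, in about 20–25 people; and one form of a declared outcome, continuous usage, has no test. The missing test follows from the text alone.

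The size of the power loss rests on joint normality, correlations of 0.5–0.6 and median cuts, all assumed. On that basis the loss is substantial: about 43–67% (Fisher) or 37–47% (chi-squared) when both variables are cut, and about 28–52% or 20–22% when only the predictor is cut against yes/no acceptance. Aim 1 is unaffected. Keeping the variables numeric improves Aim 2 but does not make it well powered.

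**What to change.** Amend the Aim 2 text in Section 7 as follows.

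- Keep age, self-efficacy, coping, spirituality and disease duration numeric in the tests.
- For continuous usage, use Spearman correlation with a 95% confidence interval for numeric predictors, and Mann–Whitney for two-level factors such as education.
- For two-level acceptance or two-level usage, use Mann–Whitney for numeric predictors. Education against a two-level outcome stays a Fisher or chi-squared comparison.
- Define the acceptance levels and the categorical usage measure before the data are seen. If the survey items can be shown to form one scale, use the ordered score with Spearman instead.
- Analyse disease activity as a numeric score within Crohn's disease and ulcerative colitis separately, or keep its stated cut. Either way, first reconcile the ulcerative colitis index: Table 1 names the Simple Clinical Colitis Activity Index, while Section 7 names Mayo sub-scores under both aims. The separate disease groups will be small.
- Keep the listed cut-points for descriptive tables, and label Aim 2 exploratory, reported as estimates with intervals.

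The cost is a short change to the analysis text and no new data beyond settling the index. The downsides are that results are slightly less simple to present than 2x2 tables, and that power stays limited. Spearman looks for a steady rise or fall, which fits the directional hypotheses the plan lists.
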